## Secondary endpoints

*By evaluating these primary and secondary endpoints using paired-measurement statistical tests, the ESCAS study will provide a comprehensive assessment of the efficacy and safety of Cerebrolysin in the treatment of aphasia after acute ischemic stroke. This will help to inform clinical decision-making and guide future research in this area*

### Efficacy

- Comparison of the National Institutes of Health Stroke Scale (NIHSS) scores between the Cerebrolysin and placebo groups at each time point (30, 60, and 90 days after study inclusion) compared to baseline. The NIHSS is a widely used tool for assessing stroke severity and neurological deficits. Paired-measurement statistical tests will be used to analyze the NIHSS scores for each time point compared to baseline, in each group. Unpaired-measurement statistical tests will be used to determine the differences between efficacy of the treatment between groups, at each time point.
- Comparison of the modified Rankin Scale (mRS) scores between the Cerebrolysin and placebo groups at each follow-up time point (30, 60, and 90 days after study inclusion), as well as comparisons between the scores at 3rd and 4th visits compared to 2nd visit. The mRS is a commonly used measure of global disability and functional outcome in stroke patients.
- Comparison of the Barthel Index (BI) scores between the Cerebrolysin and placebo groups at each follow-up time point (30, 60, and 90 days after study inclusion), as well as comparisons between the scores at 3rd and 4th visits compared to 2nd visit. The BI is a measure of functional independence in activities of daily living.

### Safety

- Incidence of AEs, SAEs and specific types of AEs. These safety endpoints will be used to evaluate the tolerability and safety profile of Cerebrolysin in the study population.

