## Coding systems utilized

The original database uses the following variables which are of interest for the data analysis. In the following list, unless otherwise noted, x represents the moment of measurement (1=baseline, 4=last visit at 90 days after treatment). Note that for Barthel Index and modified Rankin Scale, only scores at visits 2, 3, and 4 (30, 60 and 90 days after baseline, respectively) are available, with no value at baseline.

- RDMNUM = randomization number (unique to each participant)
- 
- Western Aphasia Battery
  - WABAQ\_x = Aphasia Quotient (0-100%)
- NIH Stroke Scale (Score)
  - NIHSST\_x = total score (0-42)
- Barthel Index
  - BIT\_x = total score (0-100)
- Modified Rankin Scale

- MRS\_x = total score (0-6 where 0=no symptom and 6=dead)

AEs and SAEs were stored in a separate database, from which we will retrieve the following information:

- Randomization number
- Whether the AE represents a SAE or not
- Based on the nature of the AE, some will be further classified by a clinician as being of the following nature:
  - Neurological
  - Psychiatric
  - Cardiovascular
  - Renal
  - Hematological
  - Gastrointestinal
  - Metabolic
  - Respiratory
  - Immune-related
  - ENT
  - Ophthalmic

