#### Osteoarticular

For ease of data analysis, the statistician will convert the scores from the original database to a “long” format, with the following columns:

- RDMNUM
- Visit (1/2/3/4)
- is\_crb
- is\_PP
- WABAQ
- dWABAQ \*
- NIHSST
- dNIHSST \*
- BIT \*
- MRS \*

Columns starting with a *d* represent changes in scores at visits 2/3/4 compared to visit 1 (baseline). Columns marked with \* have values only for visit 2/3/4.

The column *is\_crb* will have a true/false value, depending on whether the patient was assigned to the treatment or placebo group. The column *is\_PP* will have a true/false value, depending on whether the specified data point will be analyzed as part of the *Per Protocol* analysis set. This is a mechanism through which the statistician or any other authorized person can exclude specific patients from each analysis set, depending on criteria such as protocol violations or patient withdrawal, and then prepare the subset for the statistical analysis routine. Assignment of each patient to the correct analysis sets is described later in this document.

AE-related data will be coded and analyzed in a separate database, with the following structure:

- RDMNUM
- SAE (is the AE a SAE?)

- AE\_total (the number of total AEs accused by the patient)
- SAE\_total (the number of total SAEs accused by the patient)
- Number of AEs accused by the patient, by category
  - AE\_cardiovascular
  - AE\_renal
  - ...

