## Treatment schedule

- Treatment Cycle 1 – 30 ml Cerebrolysin/saline and ST for 2 x 5 days (2 weeks)
  - Study days 1 – 14
  - 30ml Cerebrolysin/saline i.v.
  - 1h Speech Therapy
- Treatment Cycle 2 – 30 ml Cerebrolysin/saline and ST for 2 x 5 days (2 weeks)
  - Study days 29-42
  - 30ml Cerebrolysin/saline i.v.
  - 1h Speech Therapy
- Treatment Cycle 3 – 30 ml Cerebrolysin/saline and ST for 2 x 5 days (2 weeks)
  - Study days 57-70
  - 30ml Cerebrolysin/saline i.v.
  - 1h Speech Therapy

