## Safety analysis in safety population

The Safety Population (SP) includes all trial participants who were registered in the trial and received at least one dose of treatment, irrespective of their subsequent adherence to the protocol or premature discontinuation. Unlike ITT, SP analysis focuses on AEs and SAEs caused by the treatment, thus evaluating the safety-related parameters of the products. Patients are included in this population irrespective of missing data or premature discontinuation.

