## Planned tables and graphs

### Planned tables

- table1demographics.xlsx: demographics and baseline characteristics of each group; this table will also contain the results of the statistical tests done for comparability between groups
- 
- itt/3dWABAQ.xlsx: WAB Aphasia Quotient differentials at visits 2/3/4, comparisons with baseline and comparisons of differentials between groups, at each visit
- itt/4dNIHSST.xlsx: NIHSS differentials at visits 2/3/4, comparisons with baseline and comparisons of differentials between groups, at each visit
- itt/5BIT.xlsx: Barthel Index scores at visits 2/3/4, comparisons of differentials from visits 3/4 against visit 2, and comparisons of those differentials between groups, at visits 3/4
- itt/6MRS.xlsx: modified Rankin Score at visits 2/3/4, comparisons of differentials from visits 3/4 against visit 2, and comparisons of those differentials between groups, at visits 3/4
- pp/3dWABAQ.xlsx: WAB Aphasia Quotient differentials at visits 2/3/4, comparisons with baseline and comparisons of differentials between groups, at each visit
- pp/4dNIHSST.xlsx: NIHSS differentials at visits 2/3/4, comparisons with baseline and comparisons of differentials between groups, at each visit

- pp/5BIT.xlsx: Barthel Index scores at visits 2/3/4, comparisons of differentials from visits 3/4 against visit 2, and comparisons of those differentials between groups, at visits 3/4
- pp/6MRS.xlsx: modified Rankin Score at visits 2/3/4, comparisons of differentials from visits 3/4 against visit 2, and comparisons of those differentials between groups, at visits 3/4
- AE\_table.xlsx: counting of total AEs, SAEs and specific AE categories, as well as statistical tests between groups.

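### AE incidence is meant to show tolerability, but no planned output reports infusions received or infusions stopped because of an AE

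*SAP*

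**What the plan says.** The Safety part of the SAP's secondary endpoints names "Incidence of AEs, SAEs and specific types of AEs" and gives their purpose: "These safety endpoints will be used to evaluate the tolerability and safety profile of Cerebrolysin in the study population".

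Under Treatment schedule, each of three cycles is "30 ml Cerebrolysin/saline and ST for 2 x 5 days (2 weeks"). The Safety Population takes everyone with at least one dose, "irrespective of their subsequent adherence to the protocol or premature discontinuation", so the plan expects that some patients will stop early.

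The AE data are described under Coding systems utilized: "AEs and SAEs were stored in a separate database, from which we will retrieve the following information". The list that follows holds the randomization number, SAE status and a clinical category. The AE analysis dataset, described just after that list, holds the patient number, "SAE (is the AE a SAE"), total AEs, total SAEs and counts by category. The one planned safety table, `AE_table.xlsx`, is for "counting of total AEs, SAEs and specific AE categories, as well as statistical tests between groups".

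**The concern.** Tolerability concerns whether patients can stay on a treatment as well as whether they have events on it. Under this plan, a patient who gives up after the first infusion because of a non-serious AE is recorded in the same way as one who has a mild AE of the same category and completes all 30.

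At stake is the tolerability statement in the clinical study report. If more Cerebrolysin than placebo patients stopped because of AEs, the planned outputs would give no row that says so. Readers of the efficacy tables would also lack a summary of how much treatment each arm received.

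**Working it through.** **Step 1. Planned infusions.** From Treatment schedule: 3 cycles x 2 blocks x 5 days = 30. The SAP does not print this total.

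**Step 2. Search for an exposure or stopping item.** Each place where one could stand:

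| Place in the SAP | What it holds | Infusions received | Stopped because of AE |
|---|---|---|---|
| Fields retrieved from the AE database | number, SAE status, category | no | no |
| Long-format efficacy dataset | visit, arm, `is_PP`, scores, differentials | no | no |
| AE analysis dataset | SAE flag, totals, category counts | no | no |
| Exploratory statistics (safety tests) | patients with an AE, SAE or AE class; AEs and SAEs per patient | no | no |
| Planned tables and graphs | one AE table, three AE bar plots | no | no |
| R code | arm, PP flag, SAE flag, category flags, counts | no | no |

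**Step 3. Indirect traces.** There are two. The efficacy tables print the valid N by arm and visit. The `is_PP` flag can exclude patients "depending on criteria such as protocol violations or patient withdrawal", but it is a single true/false value without a reason. Either could hint at an imbalance; neither separates AE-related stopping from other causes.

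**Step 4. What a direct row could show (assumed rates).** The SAP gives 60 patients per arm but no AE or stopping rates, so every rate below is an assumption. Power is by exact binomial enumeration under the code's own rule for a 2 x 2 table: uncorrected Chi2 if all expected counts are at least 5, otherwise Fisher; two-sided 0.05.

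| Assumed true stopping rates because of AE | Power at 60 per arm |
|---|---|
| 10% v 2% | 0.32 |
| 15% v 5% | 0.44 |
| 20% v 5% | 0.72 |
| 25% v 5% | 0.90 |

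If any-AE incidence is 50% in both arms, the planned any-AE test rejects in 5.5% of trials, whatever the difference in stopping.

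**Step 5. One selected example.** Suppose 30 of 60 patients in each arm have an AE, all non-serious, and 6 Cerebrolysin v 0 placebo patients stop because of one.

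- The any-AE row reads 50% v 50%, and the SAE row reads 0 v 0.
- The stopping row would read 6/60 = 10% v 0/60 = 0%. Expected stoppers are 6/2 = 3 per arm, below 5, so the rule selects Fisher: p = 2 x C(60,6)/C(120,6) = 0.027.
- Newcombe interval: the Wilson limits are 0.047 to 0.201 for 6/60 and 0 to 0.060 for 0/60. Lower limit = 0.10 - sqrt((0.10 - 0.047)^2 + 0.060^2) = 0.020. Upper limit = 0.10 + (0.201 - 0.10) = 0.201. The difference is 10 points, 95% CI 2 to 20.

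Six is the smallest count against zero that reaches p<0.05; 5 v 0 gives p=0.057. The example shows that the gap can matter. It does not estimate how often it would.

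**The case against.** The strongest reply is that the plan is consistent with itself. Tolerability is not a listed endpoint: it appears in one sentence on what the safety endpoints are for, and the objectives define safety as a comparison of AE and SAE incidence. Dataset, tests, table and code all follow that line. This stands, and it limits the point to a stated purpose that the outputs serve only in part.

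Three stronger readings are tempting, and the SAP does not support them.

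- **That AEs are only counted.** The plan also tests the proportion of patients with any AE, any SAE and each of twelve classes. If the stopping events fell in one class that was otherwise empty, that class row would show the same 6/60 v 0/60. The example in the working hides the imbalance only if the events also balance across classes.
- **That unequal stopping would stay wholly hidden.** A patient who stopped after one infusion would be expected to leave the Per Protocol set, so its N might read about 54 v 60 in that example. The imbalance would be visible; its cause would not.
- **That the data are not collected.** The code takes the SAE flag from column 3 of the AE source file and the category flags from columns 11 to 22, so other columns exist that the SAP does not describe. Action taken may be among them, and the protocol may cover it. What can be said is that the SAP neither retrieves nor reports it.

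Reduced exposure in the Intention To Treat analysis is not a flaw either. The SAP deliberately includes non-compliance and dropouts there.

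**Conclusion.** The point holds in a limited form. The SAP assigns AE and SAE incidence to the evaluation of tolerability, yet no listed dataset, output or code block reports AE-related stopping or infusions received out of 30. An imbalance could be seen only through valid N or the Per Protocol set, where it cannot be told apart from other reasons for loss.

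The size cannot be fixed from the document, because no stopping rates are given. Under the assumed rates, power at 60 per arm runs from 0.32 to 0.90, so the added rows would be descriptive unless the difference is large. The trial is exploratory, and neither the efficacy tests nor the existing safety tests need to change. This is a cheap improvement to what the trial can say about tolerability; it is not an error in the planned tests.

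**What to change.** 1. Add two variables per `RDMNUM` to the AE analysis dataset: infusions received (0-30), and study infusions permanently stopped because of an AE (yes/no). Take them from the dosing and withdrawal records that judging Per Protocol adherence should already require.
2. Add two rows to `AE_table.xlsx`, by arm in the Safety Population: number and percentage stopped because of an AE, with the difference and 95% CI; and median (Q1-Q3) infusions received.
3. The AE code builds its table from every row of `db_assign`. Subset it to patients with at least one dose, using the new infusion count, so that the rows match the stated Safety Population.
4. State in the Safety section that tolerability will be judged from these descriptive rows together with the planned AE and SAE incidence. They supplement that evidence and do not replace it.

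The cost is SAP wording, two variables, two table rows and a modest code change that includes the subsetting. The limit is low precision at 60 per arm, which is why the difference should be reported with its interval and not judged on a p-value alone.

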## Statistical analysis

For comparing numeric values of paired samples, differential values for each pair of values will be computed. Then, the distribution of those differentials will be compared with the normal distribution, using the Shapiro-Wilk test. If the differentials are normally distributed, we will use a one-sample Student T test (equivalent with the Student T test for paired samples) with null hypothesis  $\mu=0$ . If the differentials are not normally distributed, we will use a Wilcoxon signed-rank test with null hypothesis location=0.

For comparing numeric values of unpaired samples the normality of the values in each sample will be tested using Shapiro-Wilk test. If values from both samples are normally distributed, then variance equality between the samples will be assessed using the Bartlett test.

If the variances are equal, then the differences between the two samples will be assessed using a Student T test for unpaired samples and equal variances. If the variances are not equal, then a Student T test for unpaired samples and unequal variances will be used. In both cases, the null hypothesis will be that mean difference is equal to 0. If values from at least one of the samples are not normally distributed, then a Wilcoxon rank sum with null hypothesis of location difference equal to 0 will be performed.

For comparing ordinal values of paired samples, a Wilcoxon signed-rank test will be used, and for unpaired samples, a Wilcoxon rank-sum test will be used.

For comparing the difference in prevalences of variants of one dichotomous or nominal variable, among the groups of another dichotomous or nominal variable (i.e. testing the association between two dichotomous/nominal variables), the Chi test will be used or, where its assumptions would be violated (mainly due to small number of patients in any group), Fisher exact test will be used.

Where applicable, the two-tail p-value is reported. The type 1 error is assumed to be  $\alpha=0.05$ , and as such, results were considered statistically significant for  $p<0.05$ .

## Analysis sets

The statistical analysis will be done separately and will be reported for each of the following study populations. Assessment of inclusion and exclusion will be done independently for each patient and each analysis set. Each patient will be included in all the relevant analysis sets.

Of mention is the fact that the same statistical procedures will be applied to the PP and ITT populations, the difference being in the selection of patients based on subsetting the database.

### Efficacy analysis in Per Protocol population

The Per Protocol population (PP) includes all trial participants who have adhered to the study protocol, received the medication corresponding to the group they were assigned to after randomization, had at most minimal protocol deviations, and no missing values for total scores of Western Aphasia Battery and NIHSS at visits 2, 3 or 4, or missing values for modified Rankin Scale and Barthel Index at visits 3 or 4. This analysis set is used to assess the efficacy of the treatment in ideal conditions. From a missing data handling point of view, the PP population is subject to listwise deletion, meaning that a patient missing one data point is not taken into consideration in any analysis.

### Efficacy analysis in Intention To Treat population

The Intention To Treat (ITT) population includes all trial participants who were registered in the trial and were randomized, irrespective of their subsequent adherence to the protocol or premature discontinuation. As such, compared to PP, ITT contains all the PP subjects, as well as subjects with major protocol deviations. This analysis set is used to assess the efficacy of the studied treatment, taking into consideration patients not adhering to the protocol (non-compliance,

dropouts, SAEs, unforeseen events), thus better representing the expected results of the treatment in clinical practice. From a missing data handling point of view, the ITT population is subject to pairwise deletion, meaning that a patient missing one data point is still taken into consideration in any analysis that does not require the missing data point.

## Safety analysis in safety population

The Safety Population (SP) includes all trial participants who were registered in the trial and received at least one dose of treatment, irrespective of their subsequent adherence to the protocol or premature discontinuation. Unlike ITT, SP analysis focuses on AEs and SAEs caused by the treatment, thus evaluating the safety-related parameters of the products. Patients are included in this population irrespective of missing data or premature discontinuation.

## Data Review

### Data management and transfer

In order to execute the statistical analysis, the statistician shall have access to the electronic database summarizing the CRFs of all patients included in the study. The data transfer shall be done through secure electronic means, such as e-mail or specific file sharing utilities. At no point in time should data be accessible on public servers, unsecured by credentials.

The statistician is required to keep the minimal number of copies of the study data on their devices, in order to facilitate the statistical analysis as well as easy restoration of the data in case of data loss.

After the finalization and delivery of the CSR and other relevant materials, the statistician is entitled, but not required to keep two copies of the database, statistical analysis routines, computer code, results or other materials resulting from their activity, for personal archiving reasons. The study coordinator is entitled to ask for a copy of this data, or request the statistician to permanently erase this data from their personal devices, up to one year after the delivery of the materials.

### Data eligibility

Before unblinding, the statistician, having access to this SAP, will inspect the unblinded data to ensure correct format. Any abnormalities will be discussed and solved preferably before unblinding. After unblinding, a second round of data inspection will be performed, and if required, corrections to the SAP will be issued.

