## Software utilized

We will use Microsoft Excel 2019, part of Microsoft Office 2019 suite (Microsoft Corporation, Redmond, WA), for data preparation and cleanup.

We will use R v. 4.3.1 (R Core Team, Vienna, Austria) and RStudio (Posit Software, PBC, Boston, MA) for data analysis. In the R workspace, we will load the following libraries:

stringr	Wickham H. stringr: Simple, Consistent Wrappers for Common String Operations [Internet]. 2022. Available from: https://CRAN.R-project.org/package=stringr
ggplot2	Wickham H. ggplot2: Elegant Graphics for Data Analysis [Internet]. Springer-Verlag New York; 2016. Available from: https://ggplot2.tidyverse.org
readxl	Wickham H, Bryan J. readxl: Read Excel Files [Internet]. 2023. Available from: https://CRAN.R-project.org/package=readxl
xlsx	Dragulescu A, Arendt C. xlsx: Read, Write, Format Excel 2007 and Excel 97/2000/XP/2003 Files [Internet]. 2020. Available from: https://CRAN.R-project.org/package=xlsx

Should additional libraries be required in processing of the data analysis, they will be mentioned and their use will be motivated in the CSR.

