## Randomisation

Randomisation was discussed at length in the CSP. Briefly, patients meeting inclusion and exclusion criteria will obtain a random number corresponding to the random list generated in advance by a biometrician selected by the Coordinator. Three opaque randomization envelopes will be distributed: to the nurse in charge of preparing the infusion solution, to the study center in case of suspicion of harm to the patient, as well as to the study coordinator.

The study and database will be unblinded after closure of the database and determination of the analysis populations.

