## Source code

Supplementary file 1 is provided at the end of this SAP, representing the source code for statistical analysis using R. Ideally, this code should not be changed after unblinding. Still, due to discrepancies between databases before and after unblinding, minimal adjustments to the statistical routines (especially for data loading) might be required. All subsequent source code changes should be documented, and the final source code version used in statistical analysis should be made available together with the CSR.

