# AE preprocessing ----
# NB: if the AE classification is not complete, i.e. there are still NAs, fill them with the following
command (pay attention to which columns you execute this on)
for(i in 11:22) db_advers[is.na(db_advers[,i]),i]<-0

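### The SAP closes the database before unblinding, yet asks only that data abnormalities be solved 'preferably' before unblinding and lets AE and SAE coding still be open when the analysis code runs

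*SAP*

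**What the plan says.** Four places in the SAP bear on when the data become final.

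- **Randomisation** fixes the order: "The study and database will be unblinded after closure of the database and determination of the analysis populations".
- **Data eligibility** (under Data Review) describes a first inspection, before unblinding, in which the statistician "will inspect the unblinded data to ensure correct format". It goes on: "Any abnormalities will be discussed and solved preferably before unblinding". It then adds: "After unblinding, a second round of data inspection will be performed, and if required, corrections to the SAP will be issued".
- **Coding systems utilized** leaves the assignment of some AEs to a body-system class to a clinician. It does not say whether this is done before or after unblinding.
- **Supplementary file: R source code, AE preprocessing** provides for the case "if the AE classification is not complete, i.e. there are still NAs". Blank AE classes are then set to 0. A second comment does the same for blank SAE status, which becomes 'no'.

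The affected fields feed reported between-arm results. Under Exploratory statistics, the WAB and NIHSS changes are compared between groups at each visit. The incidence of AEs, SAEs and AE classes is compared by chi-squared or Fisher's exact test, and the number of AEs and SAEs per patient by the Wilcoxon rank-sum test.

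**The concern.** If the database is closed before the arm is revealed, nothing should remain to be solved afterwards. A rule that only prefers earlier resolution implies that some abnormalities may still be open at unblinding. The two sections cannot both govern.

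What is at stake is selective handling. Once the arm is visible, a surprising WAB value may be questioned more readily in one arm than in the other, and a borderline AE may be classed or graded with the allocation in mind. Nobody need intend this for it to bias the comparison, and an unchanged set of tests gives no protection because the bias enters through the data. AE class is the more exposed field, since it rests on a clinician's judgement and the SAP sets no deadline for it.

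**Working it through.** The SAP gives no figure on this point, so the check is mainly a comparison of its sections.

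**Step 1: order of events.** Randomisation gives database closed, populations determined, then unblinding. Data eligibility gives inspection, abnormalities solved if possible, unblinding, then a second inspection. The first order leaves no open abnormality at unblinding and the second allows one. This is a direct conflict.

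**Step 2: scope of the permission.** The first inspection is for format. The sentence on solving covers any abnormality and carries no such limit. The second inspection names one output, corrections to the SAP. No section says that data values are frozen at closure, and none says that they may be changed after unblinding.

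**Step 3: state of the data at the first inspection.** Unblinded data cannot be inspected before unblinding. This is probably a slip for blinded data, but it stands in the paragraph that controls access to the allocation.

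**Step 4: AE and SAE fields.** The code comments accept that these fields may be incomplete when the code runs. With no timing for the clinician's classification, the SAP does not exclude classification with the arm known.

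**Step 5: a hypothetical size.** Assumptions: no true effect, normal outcomes, 60 patients per arm (120 in all), two-sided Mann-Whitney test at 0.05. The k least favourable values (lowest in the active arm or highest in placebo, best split) are set aside with the arm known. Three simulation runs, two of 4,000 trials and one of 20,000, gave this chance of a significant result favouring Cerebrolysin:

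| Values set aside (k) | Range over the three runs |
|---|---|
| 0 | 2.2-2.4% |
| 1 | 3.1-3.6% |
| 2 | 5.0-5.5% |
| 3 | 7.0-8.0% |

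In the 20,000-trial run, k = 2 gives 5.0 / 2.2 = 2.3 times the rate with untouched data, from 2 / 120 = 1.7% of the values. The spread between runs is about what simulation error produces.

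**The case against.** The strongest reply is that the permission rests on one adverb. The first inspection concerns format, the only named output after unblinding is a correction to the SAP, and lock, query and audit rules commonly sit in a protocol or data management plan that is not shown. Much of this stands. It limits the point to a conflict within the SAP's own text, and that conflict remains.

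Several stronger readings are tempting, and the document does not support them.

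- **That outcome values are expected to change after unblinding.** The Source code section does speak of changes "due to discrepancies between databases before and after unblinding". The sentence goes on to minor code adjustments, mainly for data loading. The code comments explain that a test assignment file is in use and that the loading code will be adapted to the format of the real one. This is not evidence of edited WAB or AE values.
- **That clean-up is done by hand, unblinded and without trace.** Software utilized says only: "We will use Microsoft Excel 2019, part of Microsoft Office 2019 suite (Microsoft Corporation, Redmond, WA), for data preparation and cleanup". It does not say by hand and does not place clean-up after unblinding. An audit trail may be described elsewhere. Scripted cleaning in R would be a preference, not the correction of an error.
- **That the blank-fill commands are themselves biased.** They are a fixed, visible rule applied alike to both arms. Since only some AEs are to be classified, a blank may also simply mean that the class does not apply. The commands matter only because they show that coding may still be open at analysis.
- **That the double blind is defeated.** With unblinding after closure, treatment and assessment would already have been completed blind. The exposure is in data handling.
- **That the simulated rates are the expected inflation.** They model deliberate removal of the worst values, which no section permits: the ITT set keeps all randomised patients, and the populations are fixed before unblinding. Normal outcomes would also usually lead to a t test under the SAP's own rule.

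**Conclusion.** The concern holds as a contradiction between Data eligibility and Randomisation, made worse by AE and SAE coding that has no deadline. The SAP as worded permits abnormalities to be resolved with the arm known. It does not state that this is intended, and no actual bias can be inferred.

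The documents do not allow an expected size to be given. The simulated figures are a hypothetical ceiling for setting aside up to three values in the way described, and do not measure this plan. They show only that a handful of values among 120 is enough to matter, so the freeze should be a requirement.

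The consequence is moderate. The trial is exploratory and plans no confirmatory analysis, but its between-arm WAB and safety results will still be reported with p-values. The conclusion rests on the SAP alone. A lock rule in an unseen document would lower the practical risk, but the two SAP sections would still need to be reconciled.

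**What to change.** In Data eligibility:

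1. Delete *preferably*, and change *unblinded data* in the first inspection to *blinded data*.
2. Require that all data abnormalities are resolved, and that the AE class and SAE fields are complete, before the database is closed and the arm revealed. Refer to Randomisation for the order. Complete should mean an explicit entry for each AE, so that a blank no longer stands for either 'does not apply' or 'not yet judged'.
3. State that no value in the closed file is changed after unblinding unless a true error comes to light. In that case log the old value, the new value and the reason, and report the WAB Aphasia Quotient and AE/SAE results on both the closed and the corrected data.

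In Coding systems utilized, add that the clinician's AE classification is completed before unblinding.

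The cost is a few sentences of SAP text, and no statistical test changes. The one practical downside is that unblinding must wait until open queries and AE coding are finished.
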